### 3.6. Timing of final analyses – timeline of study

Allocation was revealed after the last data collection time point of the last participant enrolled. Analysis followed after this point.

### 3.7. Timing of outcome assessments

Outcome assessments were undertaken at baseline, prior to surgery, immediate recovery parameters were measured in recovery at 15 and 40 minutes following the cessation of anesthesia. Outcomes were also measured at days 1, 3, 7, 14 and 1 and 3 months.

## 4. Statistical Principles

### 4.1. Statistical significance

A two-sided  $P < 0.05$  defined significance for the primary outcome.

### 4.2. Adjustments to the statistical significance

$P < 0.01$  defined significance for secondary outcomes in order to reduce the risk of type I error.

### 4.3. Confidence intervals

95% Confidence intervals were reported for all effects where appropriate.

### 4.4. Adherence and Protocol deviations

- a. Adherence to protocol was defined by the correct allocation at the correct dose at the correct time.
- b. Adherence was presented in the CONSORT flow chart.
- c. Protocol deviations were recorded as incorrect dose or timing, or supplemental use of midazolam.

### 4.5. Definition of analysis populations

Patients were analyzed on an intention-to-treat basis.

## 5. Trial Populations

### 5.1. Screening

Patient screening was performed by a researcher who was not part of the treating team. The screening log was collected and stored as an excel file on the University of Melbourne server. This includes the reasons for screening failure and date of screening.

### 5.2. Eligibility Criteria

#### Inclusion:

1. Adult participants undergoing operative gynecological or abdominal surgery under general anesthesia of at least 1 hour duration

#### Exclusion:

1. Participants, who are not fluent in English will be excluded, as they may be unable to answer the recovery questionnaire adequately.
2. Participants undergoing diagnostic laparoscopy only
3. Participants <18 years of age
4. Current pregnancy
5. Known allergy to rocuronium, neostigmine or sugammadex, or desflurane

### 5.3. Recruitment

A CONSORT flow diagram was constructed to illustrate the flow of recruitment throughout the study.

Recruitment was performed by a study investigator who was not part of the treating team and remained blinded to the allocation. Written informed consent was obtained prior to allocation.

#### 5.4. Withdrawal

Withdrawal of the patients can occur at any point from the initial baseline up to the final completion of the study for that particular participant at 3mths after surgery, this may be in the form of refusing to continue with the study. Patient are lost-to-follow up if they are not present for their follow-up assessments in their final timepoint at 3 months.

#### 5.5. Baseline Patient Characteristics

The following characteristics was summarized in a table format as either Mean  $\pm$  SD (continuous data) on (%) (discrete data): Age, Gender, ASA status, Obesity, Education, Alcoholic consumption, Smoking status, Pre-existing conditions, Problems with previous anesthesia, Employment Status..

## 6. Analysis

### 6.1. Outcome definitions

#### **Primary outcome**

The most sensitive recovery domain of the Postoperative Quality of Recovery Scale to the effects of short acting drugs and avoidance of neostigmine is cognition. The primary outcome was the cognitive domain at 1 week after surgery, where it is expected that most of the acute inflammation will have resolved, and analgesia requirements would be minimal.

#### **Secondary outcomes**

1. Recovery for all domains and within domains at the other time points of measurement (15 minutes, 40 minutes 1 day, 3 days, 1 and 2 weeks, and 3 months following cessation of anesthesia). The domains of recovery are physiological, nociceptive, emotive activities of daily living, cognitive and overall patient perspective.

2. Compliance with protocol to ensure deep block or light/moderate block, and correctly assigned anesthetic.

3. Anesthesia, surgical (first incision to last stitch), operating room, and PACU times, and hospital length of stay

4. Incidence of persistent neuromuscular block (TOF < 4 twitches or visible fade, or TOF ratio < 0.9) upon arrival in the PACU.

5. Surgical operating conditions measured by maximal inflation pressure required for surgery, and number of times that organ movement occurred (due to diaphragmatic movement or abdominal wall

tone), and overall surgical satisfaction using a 1-5 Likert scale (1 = very unacceptable, 2 = unacceptable, 3 = acceptable, 4 = good, 5 = excellent).

## 6.2. Analysis Methods

A Fisher's Exact test was used to analyze the primary outcome of cognitive recovery at week 1 following laparoscopic surgery. A Generalized Linear Mixed Model (GLMM) test was used to analyze the recovery within and across all domains over time, including patient satisfaction. For the secondary outcomes, GLMM was used for analysis of the recovery domains and a T test was used for continuous data.

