	
after surgery of 15%. Estimates of cognitive recovery are based on prior PostopQRS research and using multiple ages and surgical cohorts. It is estimated that the cognitive recovery for this cohort and duration of surgery will be 85% if there is good recovery. Using a two tailed estimate and Chi-squared analysis, alpha of 0.05, and power of 90%, with 1:1 allocation ratio; the sample size required to detect an absolute difference of 15% is 161 per group, which will be rounded up to a total sample size of 350 patients to account for potential non-completion of the study
 
Statistical methods
 
Variables of “recovery” are dichotomized to "recovered" or "not recovered" based on whether they have achieved baseline values or better at each of the time points when measurement is performed. A tolerance factor is included in the scoring of cognitive recovery to allow for performance variability (5). Statistical analysis for the primary outcome will be with the Chi-squared test. For the secondary outcomes of recovery over time, analysis will be performed using the a general linear mixed model to investigate group differences over time. Continuous data will be analyzed using independent samples t test, or RM ANOVA for repeated measurements. A P<0.05 will define statistical significance, and P<0.01 will define statistical significance for secondary endpoints to reduce risk of Type I error. Analysis is intention to treat.
 
Randomization
 
The randomization sequence will be produced using a computer generated randomization sequence, in unequal blocks and stratified for gynecological and abdominal surgery. Concealment will be by placing the card containing the allocation information in double opaque sealed envelopes, and concealment will be maintained until after recruitment and the patients is admitted to the operating theatre. The treating anesthesiologist will then open the envelopes to reveal the allocation. A non-participant in any process of the study will perform preparation of the envelopes. A copy of the randomization sequence will be stored in a separate databank, which is password protected and not available to the investigators until the study is complete.
 
Blinding
 
Due to the nature of the drugs, it is not possible to blind the treating anesthesiologist to the allocation, but the patient and study investigators who collect the PostopQRS data will be blinded to allocation.

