#### 3.2. Randomization

The randomization sequence was produced using a computer-generated randomization sequence, in unequal blocks and stratified for gynecological and abdominal surgery. Concealment was undertaken by placing the card containing the allocation information in double opaque sealed envelopes, and concealment was maintained until after recruitment and the patients was admitted to the operating theatre. The treating anesthesiologist opened the envelopes to reveal the allocation. A non-participant in any process of the study prepared the envelopes prior to recruitment. A copy of the randomization sequence was stored in a separate databank, which is password protected and not made available to the investigators until the completion of the study.

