#### 3.3. Sample Size

Sample size estimates were based on the primary outcome of cognitive recovery at 1 week after surgery, and a clinically important difference in cognitive recovery at 1 week after surgery of 15%. Estimates of cognitive recovery were based on prior PostopQRS research and using multiple ages and surgical cohorts. It was estimated that the cognitive recovery for this cohort and duration of surgery would be 85% if there was good recovery. Using a two-tailed estimate and Chi-squared analysis, alpha of 0.05, and power of 90%, with 1:1 allocation ratio; the sample size required to detect an absolute difference of 15%

was 161 per group, which was rounded up to a total sample size of 350 patients to account for potential non-completion of the study

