## 6.3. Missing Data

Missing Data was not expected to be substantial, so it was not imputed, and incidence of recovery was analyzed using available data only.

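### The SAP's primary test is an unstratified Fisher's exact test, although the trial was planned and sized on chi-squared and randomised by surgery type: two separate, modest losses of power

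*SAP*

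**What the plan says.** Protocol 2.7 (Statistical methods) is explicit: "Statistical analysis for the primary outcome will be with the Chi-squared test". The sample size in that section rests on the same test: "Using a two tailed estimate and Chi-squared analysis, alpha of 0.05, and power of 90%, with 1:1 allocation ratio". SAP 3.3 repeats the basis, "Using a two-tailed estimate and Chi-squared analysis, alpha of 0.05, and power of 90%, with 1:1 allocation ratio", and the result: the number needed "was 161 per group, which was rounded up to a total sample size of 350 patients".

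SAP 6.2 then names a different test: "A Fisher's Exact test was used to analyze the primary outcome of cognitive recovery at week 1". SAP 6.4 says there are no further analyses, so chi-squared does not survive even as a sensitivity analysis.

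Both documents describe allocation as made "in unequal blocks and stratified for gynecological and abdominal surgery" (SAP 3.2; same wording in Protocol 2.7). SAP 6.2 mentions surgery type neither for the primary test nor for the generalized linear mixed model (GLMM) used for recovery over time.

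Two other sections bear on the point. Under SAP 6.3 nothing is imputed and "incidence of recovery was analyzed using available data only", so the analysed number falls with each non-completer. SAP 3.6, in the past tense like most of the document, says "Allocation was revealed after the last data collection time point of the last participant enrolled" and that analysis came afterwards.

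**The concern.** There are two distinct issues.

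**The test changed.** The SAP departs from the protocol and from its own sample-size section. Fisher's test rejects less often than chi-squared, so a size calculated for chi-squared need not deliver 90% power under Fisher. With a single primary outcome judged at P<0.05, the two tests can also give opposite answers on a borderline result. The SAP is written largely in the past tense, and a reader cannot tell from the text when or why the test changed, so the report has to say which one was pre-specified.

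**The stratum is not used.** Stratified blocks balance surgery type between arms. If surgery type predicts cognitive recovery, a test that ignores it treats the balanced variation as noise and becomes conservative. If it does not, nothing is lost. This loss is unrelated to the choice of Fisher, since the protocol's chi-squared is unstratified too.

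**Working it through.** **Inputs.** Recovery 85% in the better arm, difference 15 points, two-sided alpha 0.05, power 90%, 1:1 allocation, 161 per group, 350 in total (Protocol 2.7, SAP 3.3). The 70% comparator is derived: 85 − 15. The non-completion allowance is also derived: 350 − 2 × 161 = 28 patients, and 28/350 = 8.0%.

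**Step 1: reproduce the stated size.** Pooled-variance formula, no continuity correction:

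n = [z₀.₉₇₅ √(2p̄q̄) + z₀.₉₀ √(p₁q₁ + p₂q₂)]² / d², with p̄ = 0.775

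= [1.960 × √0.34875 + 1.2816 × √0.3375]² / 0.0225 = [1.1575 + 0.7445]² / 0.0225 ≈ 160.8, rounded up to 161.

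The stated figure is reproduced, which supports 70% as the comparator.

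**Step 2: exact power of each test, no stratum effect.** All 2×2 tables were enumerated under binomial sampling at 70% and 85%.

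| Evaluable | Arms | Fisher | Chi-squared |
|---|---|---|---|
| 322 | equal (161/161) | 87.9% | 90.3% |
| 322 | 2 to 6 apart | 88.5–89.6% | 90.3–90.5% |
| 336 | equal (168/168) | 89.3% | 91.6% |
| 336 | 2 to 6 apart | 89.9–91.0% | – |
| 350 | equal (175/175) | 90.65% | 92.55% |
| 350 | 2 to 6 apart | 90.9–92.0% | 92.5–92.7% |

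At 322 the loss is 2.4 points with equal arms and 0.8–2.0 otherwise. With equal arms Fisher first reaches 90% at 172 per arm (344 in total), which leaves room for 6 non-completers out of 350 (1.7%) instead of 28.

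Exactly equal arms are a low point for Fisher, so power was also averaged over random non-completion from 175 per arm (300,000 simulated trials per rate):

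| Non-completion | Fisher | Chi-squared |
|---|---|---|
| 2% | 90.9% | 92.2% |
| 4% | 90.4% | 91.6% |
| 6% | 89.7% | 91.0% |
| 8% | 89.1% | 90.4% |

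On this basis Fisher drops below 90% between 4% and 6% loss. At the full 8% allowance it is 1.3 points below chi-squared.

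**Step 3: type I error at 322 evaluable, both arms at 77.5%.** Fisher 3.7% with equal arms and 4.2–4.3% with arms 2 to 6 apart; chi-squared 4.9–5.0%.

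**Step 4: a borderline case.** Recovery in 123/161 against 137/161 gives chi-squared P = 0.048 and Fisher P = 0.066. At the design rates with 161 per arm, the tests disagree in 2.4% of trials.

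**Step 5: ignoring the stratum.** The documents give no recovery rate by surgery type, so the gap between strata in the control arm is an assumption, varied from 0 to 30 points. Marginal rates were held at 70% and 85% with a constant treatment odds ratio and arms balanced within strata (1,000,000 simulated trials per scenario). For 161 per group and 50:50 strata:

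| Assumed gap (points) | Chi-squared | CMH | Points lost | Chi-squared type I error |
|---|---|---|---|---|
| 0 | 90.3% | 90.3% | 0.0 | 4.9% |
| 10 | 90.4% | 90.6% | 0.2 | 4.8% |
| 15 | 90.5% | 90.9% | 0.4 | 4.7% |
| 20 | 90.7% | 91.4% | 0.7 | 4.5% |
| 30 | 91.2% | 92.6% | 1.4 | 4.0% |

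CMH is the Cochran-Mantel-Haenszel test without continuity correction; its type I error was 5.0% throughout. With 70:30 strata the losses are slightly smaller (1.1–1.3 points at a 30-point gap). At 175 per group and 50:50 they are 0.0, 0.1, 0.3, 0.5 and about 1.0.

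**The case against.** The case for leaving this alone has several parts.

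- **The shortfall is small and conditional.** This stands. The 87.9% needs exactly 161 in each arm, the 8% allowance is inferred and stated in neither document, and SAP 6.3 expects little missing data. With all 350 evaluable the 90% is met.
- **Stratification is not a discrepancy.** Also right as far as it goes: the protocol's test is unstratified, so the documents agree there. An unstratified test after stratified allocation is valid, and a gap between strata as large as the trial's own 15-point target costs under half a point. Both documents do say in their background sections that type of surgery confounds recovery, but they give no figure.
- **The GLMM remark is weak.** SAP 6.2 lists no model terms at all, so a missing stratum is one part of a general lack of detail. No loss was calculated for that model.
- **A reason may exist elsewhere.** Some front pages of the SAP were not available, so only its absence from the text provided can be asserted.
- **A CMH test would be a third primary test that neither document planned.** This is a fair objection if the data were already unmasked, and the remedy has to depend on that.
- **Fisher protects the level.** True, but chi-squared is close to nominal here, at 4.9–5.0% for 322 evaluable patients.

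None of this removes the mismatch between Protocol 2.7 and SAP 3.3 on one side and SAP 6.2 on the other.

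**Conclusion.** The concern holds, at modest size. The named primary test is neither the protocol's nor the one used for the sample size. Under the 70% versus 85% assumption, using Fisher costs about 1 to 2.4 points of power at 322 evaluable patients, and the stated 90% is then not met. It is met with all 350 evaluable, and on average up to about 4% non-completion.

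Ignoring the stratum costs a further 0 to 1.4 points at 161 per group, depending on an assumed gap between strata of 0 to 30 points. That component is a missed gain, not an inconsistency between the documents. Neither issue inflates type I error. The stronger reason to act is that the choice of test can decide a borderline result, and the documents do not agree on which test governs.

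**What to change.** **If allocation is still masked:** in SAP 6.2, replace Fisher's test with a Cochran-Mantel-Haenszel test stratified by surgery type, without continuity correction. This is the stratified form of the protocol's chi-squared. Report the Mantel-Haenszel risk difference with its 95% confidence interval, and name surgery type as a fixed effect in the GLMM. The cost is SAP wording: surgery type is already recorded as the stratification factor, and the test needs only two 2×2 tables.

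**If allocation had already been revealed when the SAP was written:** keep the protocol's chi-squared as primary, state when and why Fisher was substituted, report both results, and give the CMH result as a labelled sensitivity analysis. The cost is a sentence of explanation and two extra reported results.

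**If Fisher is kept in a SAP finalised under masking:** give the reason, and restate the power in SAP 3.3 as about 88–89.6% at 322 evaluable.

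No new data are needed in any of these cases.

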## 6.3. Missing Data

Missing Data was not expected to be substantial, so it was not imputed, and incidence of recovery was analyzed using available data only.

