user-defined intervals. From some of the subsequent discriminant validation studies, time points have included early and late measures such as 15 minutes, 40 minutes, 1 and 3 days, and 3 months after the completion of anesthesia (typically defined as after the last surgical stimulation). Recovery is broadly defined as return to baseline values or better, except for the cognitive domain where a tolerance factor is included to allow for normal performance variability, such that patients are allowed to perform a little worse than baseline as still be scored as recovered (5). Because repeated tests tend to have a learning effect, the cognitive domain uses parallel forms, and only a small learning has been shown (5).

One of the most important benefits of the PostopQRS scale is that it enables recovery to be quantified and measured. This makes it possible to compare different interventions with the express purpose of developing clinical interventions to improve quality of recovery. The PostopQRS offers a tool to provide the recovery process to be examined. There are no other tools in existence that provide a comprehensive, sensitive assessment of the multiple aspects or domains of recovery, and is yet relatively simple to perform. Validation studies have been performed and show good discriminative ability (5-8). Ease of use is facilitated by using a web-based data entry system and the ability to use the telephone to conduct surveys after discharge from hospital. Telephone survey has been shown to be equivalent to face to face interviews using the PostopQRS (5). Further, the PostopQRS allows users to drill down to identify which recovery domain is affected for individuals in real time as well as for group audit.

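### As written, the available-data rule leaves patients too drowsy or unwell to be tested out of the 15- and 40-minute recovery rates, although they have not recovered on the domains that need a response

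*SAP*

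**What the plan says.** SAP 6.3 has one missing-data rule for every time point. Little missing data was expected, "so it was not imputed, and incidence of recovery was analyzed using available data only".

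Protocol 2.7 (Statistical methods) classes each recovery variable as recovered or not recovered "based on whether they have achieved baseline values or better at each of the time points when measurement is performed", with a tolerance factor for cognition.

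The early assessments fall under this rule. SAP 6.1, secondary outcome 1, is "Recovery for all domains and within domains at the other time points of measurement", and its list starts at 15 and 40 minutes. SAP 3.7 states that "immediate recovery parameters were measured in recovery at 15 and 40 minutes following the cessation of anesthesia".

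SAP 4.5 adds analysis by intention to treat, SAP 6.2 a generalized linear mixed model (GLMM) for recovery over time, and SAP 6.4 no further analyses. The text above the reference list in SAP 6.7 says that an external database scores recovery automatically. Neither document says how a patient is recorded who is due for assessment but cannot do it.

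**The concern.** The PostopQRS is an interview of about 5 to 6 minutes (Protocol 2.5). A patient too drowsy or unwell to take part soon after anesthesia has not returned to baseline on cognition or on the other domains that need an answer. The blank therefore carries information: non-recovery is the reason that there is no score. Read literally, the two rules treat this blank like a missed telephone call and remove the patient from the rate.

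At stake are the early secondary comparisons. The patients removed are among the poorest early recoverers. If one arm has more of them, its rate is raised more by their removal, so slower recovery can look like equal or better recovery.

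**Working it through.** **The plan's own figure.** The documents give no rate of untestable patients and no expected recovery at 15 or 40 minutes. The only figure to reproduce is the sample size (85% v 70%, two-sided alpha 0.05, power 90%). With pooled variance under the null and no continuity correction:

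n = [1.960 × √(2 × 0.775 × 0.225) + 1.282 × √(0.85 × 0.15 + 0.70 × 0.30)]² / 0.15² = (1.157 + 0.745)² / 0.0225 = 160.8, so 161 per group.

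This matches SAP 3.3. It concerns the 1-week outcome and does not change. The total of 350 gives 175 per arm, used below.

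**Formula for the bias.** Let R be the share of all randomized patients in an arm who have truly recovered at the time point, and u the share who are untestable, all of them not recovered.

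- Untestable patients scored as not recovered: the estimate is R.
- Available data only: the estimate is R / (1 − u).

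Where true recovery is the same in both arms, the arm with the larger u always looks better.

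**Illustration (assumed values).** R = 40% in both arms, with 5% untestable under deep block (DNB) and 20% under moderate block (ModNB):

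- Recovered: 0.40 × 175 = 70 in each arm.
- DNB: 70 / (175 × 0.95) = 70 / 166.25 = 42.1%.
- ModNB: 70 / (175 × 0.80) = 70 / 140 = 50.0%.
- False difference: 7.9 points in favour of ModNB.

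**Range (assumed values).** R runs from 30% to 50% and is equal in both arms. The last column is the share of 100,000 simulated trials of 175 per arm that reach the secondary level of P < 0.01 on a pooled z test of the available-data rates.

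| Untestable, DNB v ModNB | False difference favouring ModNB (points) | Trials with P < 0.01 |
|---|---|---|
| 5% v 5% | 0 | about 1% |
| 5% v 10% | 1.8 to 2.9 | 1.5% to 2.2% |
| 5% v 20% | 5.9 to 9.9 | 7% to 20% |
| 10% v 30% | 9.5 to 15.9 | 18% to 56% |

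Scoring untestable patients as not recovered gives a difference of 0 and about 1% rejections throughout. At equal untestable shares only the level moves: 40% becomes 0.40 / 0.95 = 42.1% in both arms.

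**The mirror case.** If 40% of the *testable* patients recover in both arms, available data show 40% v 40%. With 5% v 20% untestable, the rates among all randomized patients are 0.40 × 0.95 = 38% and 0.40 × 0.80 = 32%. The zero observed difference follows directly from the assumption of equal recovery among testable patients.

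**Does anything else in the plan repair it?** The intention-to-treat statement fixes the arm in which a patient is counted, but supplies no score. The GLMM uses the patient's later results. It can still be biased when the early value is missing because of what that value would have been. The size of the bias in the GLMM was not calculated; the table uses simple proportions.

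**Clock start.** SAP 3.7 and secondary outcome 1 count from cessation of anesthesia. The assessment paragraph in Protocol 2.5 counts from surgery. SAP 2.1 says of earlier use of the scale that completion of anesthesia is "typically defined as after the last surgical stimulation". How many patients are untestable at 15 minutes depends on which of these applies.

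**The case against.** The strongest reply is that the documents do not say these patients are recorded as missing. The database scores automatically, and the scale's own rules may already class a patient who cannot respond as not recovered. That stands: removal is what the written rules imply, not something the documents report. It does not excuse a SAP that leaves the rule unstated.

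Several stronger readings that a reader might infer are not supported:

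- *Many patients would still be anaesthetised at 15 minutes.* This fits poorly with SAP 3.7, which counts from cessation of anesthesia and places the tests in the recovery area. Protocol 2.5 also requires alertness judged safe before extubation. Drowsiness is the realistic cause.
- *The arms are known to differ in testability.* No rate is given. Protocol 2.2 expects less variance between reversal and emergence with short-acting drugs, and less residual block with sugammadex, so a difference is plausible. Against it, both arms receive desflurane and ModNB may be lightened before the end of surgery. The 47 v 95 minute anesthetic times in Protocol 2.2 concern reversal of deep block, which is not the comparator here.
- *Such patients are unrecovered on every domain.* Physiological measures can be taken in a drowsy patient.
- *A real early benefit would be reported as zero.* That holds only under the equal-recovery assumption of the mirror case. Even with correct scoring, the trial has little power there: for 38% v 32%, SE = √(2 × 0.35 × 0.65 / 175) = 0.051, 0.06 / 0.051 = 1.18, 2.576 − 1.18 = 1.40, so power at P < 0.01 is about 8%.

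It is also fair that a modest imbalance does little harm: 5% v 10% raises the false-positive rate only to about 2%.

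**Conclusion.** The point holds in limited form. As written, SAP 6.3 and Protocol 2.7 together leave patients who cannot be tested because of their clinical state out of the 15- and 40-minute rates, although they have not recovered on the domains that need a response. Whether this happens in practice depends on database scoring that the documents do not describe.

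If the untestable share differs by arm and true recovery is similar, the comparison is biased in favour of the arm with more untestable patients: by about 2 to 3 points at 5% v 10%, and 6 to 10 points at 5% v 20%. All of these shares are assumptions. With equal shares and equal true recovery there is no false difference.

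A reader might extend this to the main result. The documents do not support that. "The primary outcome was the cognitive domain at 1 week after surgery", so early drowsiness does not enter it, and 161 per group stands. In principle the same rule drops a patient who is dead or too ill to be tested at 1 week, but no rate is given and Protocol 2.2 describes mortality as very low. The primary outcome is essentially unaffected. The change is worth making because the early time points are named outcomes and the remedy is cheap.

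**What to change.** In SAP 6.1 and 6.3, state that:

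- a patient who cannot be tested at a time point because of clinical state is scored not recovered at that time point on the domains that need a patient response (cognitive and the other interview domains);
- physiological measures actually taken are kept and scored as usual;
- only assessments missed for unrelated reasons (refusal, assessor unavailable, patient not contactable) are treated as missing.

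State how the database's automatic scoring treats these patients. Define the clock start for the 15- and 40-minute points and use it in both documents. Report the number untestable by arm and time point; that table would also show whether the arms differ.

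The SAP describes data collection in the past tense, so reasons may not have been recorded. In that case add, by amending SAP 6.4, a sensitivity analysis that scores every blank 15- and 40-minute interview domain as not recovered, and set it beside the available-data result. It will also count some unrelated gaps as non-recovery, so it is a check on the result and not a replacement for it.

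The cost is a few sentences, one reason code on the assessment form and one table. Absolute early recovery rates will be slightly lower. The sample size and the primary analysis stay as they are.
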